7.4 STUDY VISITS

Not applicable.

8. VARIABLES

8.1 EXPOSURES

The exposure of this study is IV rt-PA treatment within 4.5 hours of symptom onset.

[figure not shown]
8.2 OUTCOMES

8.2.1 Primary outcomes

- Favourable outcome (mRS 0-1) at 1 year

8.2.2 Secondary outcomes

- Any intracranial haemorrhage (ICH) during hospitalisation
- All-cause mortality during hospitalisation
- Independence (mRS 0-2) at 1 year
- Distribution of mRS score at 1 year
- All-cause mortality at 1 year
- Baseline characteristics (age, gender, NIHSS, etc.)

8.3 COVARIATES

The covariates to be collected at baseline as follows:

- Demographic and sociological characteristics
 - o Age
 - o Gender (male, female)
 - o Body weight
 - o Medical insurance status (urban employee basic medical insurance, urban resident basic medical insurance, new rural cooperative medical insurance, other insurance, no insurance)
- Lifestyle related characteristics
 - o Smoking status (current smoker, former smoker, never smoker)
- Stroke severity (baseline NIHSS)
- Time from symptom onset to hospital admission
- For patients in the IV rt-PA cohort:
 - o Time from symptom onset to treatment
 - o Time from hospital admission to treatment
 - o rt-PA dosage (dichotomised as standard dosage and low dosage)
- Comorbidities at baseline
 - o Diabetes
 - o Coronary artery disease
 - o Atrial fibrillation

Proprietary confidential information © 2021 Boehringer Ingelheim International GmbH or one or more of its affiliated companies

- o Prior stroke/transient ischaemic attack
- o Hypertension
- Co-medication at baseline
 - o Anti-platelet
 - o Oral anticoagulation
 - o Lipid lowering
- Hospital level
 - o Grade 2
 - o Grade 3

Other covariates including:

- Duration of hospitalization
- Reasons for not being treated with rt-PA for rt-PA non treatment group

9. DATA SOURCES

9.1 ZSQCC PLATFORM

The current study will be conducted based on data from the ZSQCC platform, which is a continuous comprehensive reporting system that collects 100000 patient-level data from 80 stroke centres from January 2017 to March 2020.

All printed medical documents for consecutive AIS patients admitted in the stroke centre will be provided and scanned by investigators from ZSQCC. Only the de-identified scanned documents will be preserved as images in a safe information database. The local infrastructure and characteristics of each recruited centre will also be recorded.

The database includes patient demographic information, baseline clinical characteristics, indicators related to diagnosis and treatment during hospitalisation and follow-up after discharge. The platform staffs tried to follow up all discharged patients by a phone call at 1-year discharge. In addition, patients who received rt-PA treatments were followed up by a phone call at 3-month after discharge. Telephone follow-up of the platform was conducted by platform staffs. The follow-up standards were unified, and telephone recordings were all kept. Neurologists conducted trainings at regular intervals for platform staffs and randomly checked the telephone recordings. Several studies based on this dataset were approved by the Second Affiliated Hospital of Zhejiang University Institutional Review Board (IRB) and were published in peer-reviewed journals. [\[P2104780\]](#),[\[P2104783\]](#),[\[P2104784\]](#),[\[P2104779\]](#),[\[P2104782\]](#)

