## **9.5 STUDY SIZE**

A feasibility assessment was conducted in June 2020. The results showed that there were approximately 1561 elderly AIS patients who were treated with IV rt-PA and 1037 patients who were admitted to the hospital within 4.5 hours of symptom onset without IVT contraindication and did not receive reperfusion treatment from Jan 2017 to Mar 2020 according to the ZSQCC platform database.

A meta-analysis of RCTs showed that the 3-month favourable outcome (mRS 0-1) with IV rt-PA versus the placebo arm in patients above 80 years of age was 19.1% versus 13.1% (relative risk [RR]: 1.46). In safe implementation of thrombolysis in upper time window monitoring study, the 3-month favourable outcome for IV rt-PA treated elderly patients was 26.6%. In this study, we assume the 1-year favourable outcome for IV rt-PA treated elderly patients is 28%, with the same RR (1.46) observed in RCTs, and the 1-year favourable outcome for non-reperfusion cohort is 19.2%. With the treatment ratio 2:1 between the IV rt-PA cohort and the non-reperfusion cohort, 1106 patients in total are needed to detect the treatment difference of 8.8% with 90% power and a 2-sided alpha of 0.05. Considering a 15% rate of loss to visit, 1301 patients in total are needed. If a 2:1 match cannot reach good match in terms of the major potential confounders, we may conduct a 1:1 match instead. Considering a treatment ratio 1:1 with the same assumption described above with power of 90% at a 2-sided, 974 patients are needed to detect 8.8% treatment difference, considering 15% loss to visit, 1146 patients are needed in total.

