## **9.9 LIMITATIONS OF THE RESEARCH METHODS**

This is a NIS based on existing data. Although PSM is used, we cannot rule out the influence of unmeasured confounding factors. In this study, potential limitations of the study design can be listed as:

- Zhejiang is an economically advanced province in China. Patients in this study may not be fully representative to all AIS patients in China. We plan to compare the

baseline characteristics of patients in this study with those from CSCA to evaluate the representativeness of the population in this study.

- AIS patient data from the ZSQCC platform were reported by the stroke centre without external monitoring.
- The treatment adapted for AIS patients may be different among stroke centres.
- The completeness of the captured data and potential for misclassification of data could differ among stroke centres.
- Some important variables may not be collected in the database. For example, patients' education level was not available in the database. Another example is that patients who did not receive rt-PA treatments were not followed up at 3 months after discharge. Therefore, for outcomes at 3 months we could only describe them in the rt-PA treated cohort.

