10.2 HANDLING OF MISSING VALUES

For comorbidities at baseline (including diabetes, coronary artery disease, atrial fibrillation, prior stroke/transient ischaemic attack, and hypertension) and co-medication at baseline (including anti-platelet, oral anticoagulation, and lipid lowering), missing values will be regarded as absence of those comorbidity and co-medication. For medical insurance status, smoking status, and hospital level, missing values will be assigned to a separate group.

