For the secondary outcomes, descriptive summaries will be conducted in the PS-matched cohorts separately. For the categorical variables including any intracranial haemorrhage (ICH) during hospitalisation, all-cause mortality during hospitalisation and independence (mRS 0-2) at 1 year, the Chi-square test and conditional logistic regression model will be conducted. For the distribution of mRS score at 1 year, the Wilcoxon rank sum test and ordinal logistic regression model will be performed. For the all-cause mortality at 1 year, in addition to a Chi-square test, a Kaplan-Meier curve with log-rank test will be used to analyse the data. Cox regression models will be used to estimate hazard ratios (95% confidence interval) between the 2 matched cohorts.

*Note: 1 year in this analysis is defined as 12 ± 1 months.

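### Only rt-PA patients were called at 3 months; if deaths learned then count at 1 year, the SAP's chi-square for 1-year mortality compares cohorts with different death ascertainment

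*SAP*

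**What the plan says.** SAP 9.1 (and Protocol 9.4.1 in the same terms) describes two contact schedules. For everyone: "The platform staffs tried to follow up all discharged patients by a phone call at 1-year discharge". For one cohort only: "In addition, patients who received rt-PA treatments were followed up by a phone call at 3-month after discharge". Protocol 9.9 confirms that "patients who did not receive rt-PA treatments were not followed up at 3 months after discharge", and draws one consequence: "for outcomes at 3 months we could only describe them in the rt-PA treated cohort". It does not mention 1-year outcomes in this connection.

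For all-cause mortality at 1 year, SAP 11.1 says that "in addition to a Chi-square test, a Kaplan-Meier curve with log-rank test will be used to analyse the data", followed by Cox regression. Protocol 9.7.1 names only Kaplan-Meier and Cox for 1-year death; the chi-square appears in the SAP. A note to SAP 11.1 adds that "1 year in this analysis is defined as 12 ± 1 months".

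The only missing-data rule in view is SAP 10.2, which covers baseline variables. For comorbidities and co-medication, "missing values will be regarded as absence of those comorbidity and co-medication"; insurance, smoking and hospital level get a separate category. The Protocol's checklist (Annex 2, item 10.7) marks missing-data methods as not applicable. Protocol 9.5 nevertheless plans for loss: "Considering a 15% rate of loss to visit, 1301 patients in total are needed".

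**The concern.** A death is final, so a death learned at 3 months would naturally be coded as dead at 1 year. A patient found alive at 3 months and then lost is not a known 1-year survivor. Under that coding, an rt-PA patient who dies early stays in the analysis when the 1-year call fails, while a control with the same course drops out. At equal reach, the extra call can only add known deaths to the rt-PA cohort.

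The study is titled as one of effectiveness and safety, and Protocol section 7 places it in the setting of real-world evidence for extending a label to new populations. One-year mortality is a main safety figure there. Protocol 9.7 disclaims formal hypothesis testing, so what is at stake is the reported percentages and p-value, not a formal decision.

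**Working it through.** **Inputs from the documents.** Protocol 9.5 allows 15% loss, not split by cohort: 1106/0.85 = 1301.2 (stated 1301) and 974/0.85 = 1145.9 (stated 1146). At 1:1 this is 1146/2 = 573 per cohort. The plan has no mortality figure to reproduce.

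**Assumptions.** True risk is equal in both cohorts. Among patients discharged alive, 1-year mortality is m = 25%, and e = 5%, 10% or 15% die before the 3-month call, all learned at that call. In-hospital deaths are h = 0%, 5% or 10%, always known. L is the share unreached at 1 year.

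**Formulas for the observed-case analysis.**
- Known deaths after discharge: rt-PA D = e + (m − e)(1 − L); control D = m(1 − L).
- Known survivors: A = (1 − m)(1 − L).
- Observed mortality = [h + (1 − h)D] / [h + (1 − h)(D + A)].

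**Example: e = 10%, h = 5%, L = 15% in both cohorts.**
- rt-PA: D = 0.10 + 0.15 × 0.85 = 0.2275 and A = 0.6375, so (0.05 + 0.95 × 0.2275)/(0.05 + 0.95 × 0.865) = 0.2661/0.8718 = 30.5%.
- Control: D = 0.2125, so (0.05 + 0.95 × 0.2125)/(0.05 + 0.95 × 0.85) = 0.2519/0.8575 = 29.4%.
- Truth: 0.05 + 0.95 × 0.25 = 28.75%.

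Both cohorts read too high, because in-hospital deaths are never lost and survivors are. The difference is +1.2 points before rounding.

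**Equal random loss of 15%, rt-PA minus control (points).**

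| In-hospital deaths | e = 5% | e = 10% | e = 15% |
|---|---|---|---|
| 0% | +0.7 | +1.3 | +1.9 |
| 5% | +0.6 | +1.2 | +1.7 |
| 10% | +0.5 | +1.0 | +1.5 |

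With h = 0 the odds ratio is 1 + (e/m) × L/(1 − L): 1.04, 1.07 and 1.11. With 573 per cohort and h = 5%, the chance that the chi-square shows higher rt-PA mortality at the nominal two-sided 5% level is 3.9% to 8.5% instead of 2.5% (normal approximation). A second set of assumptions gives +0.4 to +2.0 points at 15% loss: 20% to 40% total mortality with 8% in hospital, 30% to 70% of later deaths before the call, and 90% of these learned.

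**Unequal but random loss: rt-PA 10%, controls 20%.** Take h = 10% and e = 5%.
- rt-PA: (0.10 + 0.90 × 0.23)/(0.10 + 0.90 × 0.905) = 0.307/0.9145 = 33.6%.
- Control: (0.10 + 0.90 × 0.20)/(0.10 + 0.90 × 0.80) = 0.28/0.82 = 34.1%.

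The difference is −0.6. Over e = 5% to 15% the range is −0.1 to +0.6 points with h = 5%, and −0.6 to +0.1 with h = 10%.

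**Kaplan-Meier, censored at last contact known alive.** For rt-PA, 1 − (1 − h)(1 − e)(1 − d/(d + A)), where d = (m − e)(1 − L) is the late known deaths. With e = 10%, h = 5%, L = 15%: d = 0.1275, d/(d + A) = 0.1275/0.765 = 1/6, and 1 − 0.95 × 0.90 × 5/6 = 28.75%. For controls, 1 − 0.95 × (1 − 0.2125/0.85) = 28.75%. L cancels within each cohort, so unequal random loss also leaves no difference.

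**Loss related to death: 30% of the dead and 10% of the living unreached in both cohorts, e = 10%, h = 0.**
- Observed-case: 0.205/0.880 = 23.3% against 0.175/0.850 = 20.6%, a difference of +2.7.
- Kaplan-Meier: 1 − 0.90 × 0.675/0.780 = 22.1% against 20.6%, a difference of +1.5.
- Ignoring the 3-month call: 20.6% in both, a difference of 0.0, although both understate the true 25%.

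**The case against.** The strongest reply is that no passage says a 3-month death is carried forward or that the chi-square is observed-case. The 1-year call was attempted for everyone discharged; if vital status is taken only from it, this source of bias disappears. That stands, and the point is conditional on the coding. The 12 ± 1 month note does not settle the matter, because it defines the time window and not the source of deaths.

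Second, a rule may exist where we cannot see it: Protocol 9.7.2 (where the checklist places sensitivity analyses), the SAP section between 11.1 and 11.3, or the separate NIS-DMRP. That also stands.

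Third, a reader might infer that the analysis is bound to be biased against rt-PA while the control figure is correct. The documents support neither. They give no reach by cohort, and similar reach is what secures the sign. The control figure is correct only if in-hospital deaths are left out, and no visible text restricts the outcome to patients discharged alive.

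Fourth, the effect is modest, concerns a secondary outcome, and Kaplan-Meier and Cox are already planned. All true. But no visible text states the censoring rule, the chi-square sits beside them with no order of precedence, and Protocol 9.9 sees the consequence of the missing call only for 3-month outcomes.

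**Conclusion.** The point holds in conditional form and is worth correcting before analysis. If deaths learned at 3 months count at 1 year and patients of unknown status are excluded, the chi-square compares cohorts with different ascertainment of death. With equal reach and 15% random loss this adds about 0.5 to 1.9 points to rt-PA mortality relative to control when the true risks are equal. Mortality, timing of deaths and reach are assumptions; only the 15% comes from the documents, and it is a planning allowance. Unequal reach can cancel or reverse the difference, so the direction is not certain.

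A reader might also infer that the primary outcome is compromised. The figures do not support that. If early deaths are carried forward as unfavourable, with 15% random loss and h = 0, the planned 28% becomes 0.28 × 0.85/0.8575 = 27.8% to 0.28 × 0.85/0.8725 = 27.3%. That is 0.2 to 0.7 points lower, and against rt-PA. In-hospital outcomes are unaffected. Confidence is medium.

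**What to change.** In SAP 11.1:

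1. Make the planned Kaplan-Meier and Cox analysis the main result for 1-year mortality, in place of the observed-case chi-square. Count in-hospital deaths as events and censor patients not known to have died at last contact known alive: discharge for unreached controls, 3 months for rt-PA patients reached only then. This is unbiased under random loss, equal or not, and matches the methods that Protocol 9.7.1 names.
2. As a sensitivity analysis, repeat it with the 3-month call ignored in the rt-PA cohort. This is valid only where a 1-year call was still attempted after a 3-month death. Otherwise it deletes those deaths: with e = 10%, 15% random loss and h = 0, 0.1275/(0.1275 + 0.6375) = 16.7% against 25.0%, or −8.3 points.
3. Report 1-year call success and the source of death information by cohort.

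If a section that is not visible already holds the rule, a cross-reference in SAP 11.1 is enough.

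The cost is SAP wording and a little programming, with no new data. The drawback is that Kaplan-Meier assumes loss unrelated to death. In the death-related example above it still leaves about +1.5 points, against +2.7 for the observed-case analysis. The sensitivity analysis sets aside known deaths and, when loss is related to death, needs a similar reach pattern in both cohorts.

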9.2 CSCA PLATFORM

The CSCA is a national, hospital-based, multicentre, voluntary, multifaceted intervention and continuous quality improvement initiative, launched by Chinese Stroke Association in 2015. This programme is made available to all Chinese grade 2 and 3 hospitals. Hospitals continued to join the programme in a staggered manner. By Jul 2019, 1476 hospitals (720 grade 2 hospitals, 756 grade 3 hospitals) had participated into this programme. Hospital characteristics, including geographic region, teaching status, hospital volume (grade 2 and 3) and annual stroke volume, are surveyed. Data were collected via the web-based patient data collection and management tool (██████████), abstracted via chart review, coded, de-identified and transmitted in a secure manner to maintain patient confidentiality compliant with national privacy standards. The following data were collected for each hospitalization: patient demographics, history of disease and medication, hospital presentation, initial neurological status, medications and interventions, reperfusion strategy and in-hospital outcomes and complications.

10. DATA MANAGEMENT AND SOFTWARE/TOOLS**10.1 SOFTWARE/TOOLS**

Propensity score matching (PSM) will be performed using R 4.0.5 (package: MatchIt) and other analyses will be conducted with SAS 9.4.

10.2 HANDLING OF MISSING VALUES

For comorbidities at baseline (including diabetes, coronary artery disease, atrial fibrillation, prior stroke/transient ischaemic attack, and hypertension) and co-medication at baseline (including anti-platelet, oral anticoagulation, and lipid lowering), missing values will be regarded as absence of those comorbidity and co-medication. For medical insurance status, smoking status, and hospital level, missing values will be assigned to a separate group.

10.3 HANDLING OF INCONSISTENCIES IN DATA AND OUTLIERS

Inconsistencies in Data and Outliers will be re-checked. If they are still abnormal (for example: age > 120; gender is neither male nor female), they will be removed from the analysis.

11. DATA ANALYSIS

11.1 MAIN ANALYSIS

[figure not shown]
Descriptive data regarding patient demographic, lifestyle-related, and clinical characteristics will be summarized. For categorical measures, data will include the frequency (number of patients with specific cases [n]) and percentage (%) of total study patients observed in each category (N). All variables will be summarized descriptively by tabular displays of mean, standard deviations, median, inter-quartile ranges, and ranges of continuous variables, and frequency distributions of categorical variables. When necessary, continuous variables also will be categorized into intervals, with the distribution of patients (n, N, %) for each interval provided. We will compare the baseline characteristics of the 2 treatment cohorts (patients who received IV rt-PA and patients who did not receive reperfusion treatment) through the absolute standardized difference (ASD) method, where at least 0.1 ASD will be considered a significant difference.

To account for potential confounding, the 2 cohorts will be 1:1 or 2:1 matched by baseline characteristics using the Propensity Score Matching method. The feasibility of PSM will be evaluated based on available sample size and descriptive results. If patient characteristic between the 2 cohorts are significantly different, i.e., less than 50% of patients in the IV rt-PA cohort can be matched to the non reperfusion cohort based on PSM, the study design will be re-evaluated before proceeding to analysis. The PSM aims to balance the 2 cohorts on baseline covariates. The propensity score model will include age, gender, baseline NIHSS/NIHSS categories (0-4, 5-10, 11-15, 16-21, and ≥ 22), medical insurance status, smoking status, hospital level, diabetes, coronary artery disease, atrial fibrillation, prior stroke/transient ischaemic attack, hypertension, anti-platelet, lipid lowering, oral anticoagulation, and time from symptom onset to hospital admission. The method of Nearest Neighbour matching will be used (a maximum caliper width equal to 0.2 of the standard deviation of the logit of the propensity score) to select the matched samples. Then we will compare the baseline characteristics of the 2 propensity-score-matched cohorts. The absolute standardized difference (ASD) between the 2 PS-matched cohorts will be calculated, where at least 0.1 ASD will be considered a significant difference. For baseline covariates that are not sufficiently balanced after PSM, they will be included in an appropriate multivariate model to adjust for those differences.

For the primary outcome, a comparison of the percentage of 1-year* mRS score (0-1) between the 2 PS-matched cohorts will be conducted using a Chi-square test. A conditional logistic regression model will be used to estimate odds ratios (95% confidence interval) between the 2 matched cohorts.

For the secondary outcomes, descriptive summaries will be conducted in the PS-matched cohorts separately. For the categorical variables including any intracranial haemorrhage (ICH) during hospitalisation, all-cause mortality during hospitalisation and independence (mRS 0-2) at 1 year, the Chi-square test and conditional logistic regression model will be conducted. For the distribution of mRS score at 1 year, the Wilcoxon rank sum test and ordinal logistic regression model will be performed. For the all-cause mortality at 1 year, in addition to a Chi-square test, a Kaplan-Meier curve with log-rank test will be used to analyse the data. Cox regression models will be used to estimate hazard ratios (95% confidence interval) between the 2 matched cohorts.

*Note: 1 year in this analysis is defined as 12 ± 1 months.

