### **9.7.1 Main analysis**

To account for potential confounding, the study cohorts (patients who received IV rt-PA and patients who did not receive reperfusion treatment) will be 1:1 or 1:2 matched by baseline characteristics using the PSM method. The PSM aims to balance the 2 treatment cohorts on baseline covariates. The feasibility of PSM will be evaluated based on available sample size and descriptive results. If patient characteristic between the 2 cohorts are significantly different, i.e., less than 50% of patients in the IV rt-PA cohort can be matched to the non-reperfusion cohort based on PSM, the study design will be re-evaluated before proceeding to analysis. The Nearest Neighbour method of PSM will be used to select the matched samples. The final list of baseline characteristics in the PSM will be decided in conjunction with BI. All variables listed in the covariates will be considered. Covariates including duration of hospitalization and reasons for untreated with rt-PA are only for descriptive analysis. The distribution of baseline characteristics will be presented before and after the matching process. Absolute standardized difference (ASD) between the compared groups will be calculated, in which a  $\geq 10\%$  ASD will be considered a meaningful difference. For baseline covariates that are not sufficiently balanced after PSM which is assessed using ASD, the covariates will be included in an appropriate multivariate model to adjust for those differences.

For the primary outcome, a comparison of 1-year mRS 0-1 score between the 2 propensity score (PS)-matched cohorts will be calculated using a chi-square test. A logistic regression model will be used to calculate odds ratios between 2 matched cohorts.

For the secondary outcomes, descriptive summaries will be conducted in the PS-matched cohorts separately. For categorical variables including any ICH during hospitalisation, mortality during hospitalisation, and mRS 0-2 at 1 year, the percentage and 95% confidence interval will be calculated. A logistic regression model will be used to calculate the odds ratios.

For time to death up to 1 year and time to ICH during hospitalisation, a Kaplan-Meier curve will be used to analyse the data. Cox regression will be used to estimate hazard ratio for 1-year all-cause mortality between PS-matched cohorts.

For the distribution of mRS, an ordinal logistic regression model will be used to calculate the odds ratio between the PS-matched cohorts.

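### If 2:1 matching keeps incomplete sets, the unweighted chi-square, rank-sum and survival comparisons retain confounding, and the SAP leaves open whether it will

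*SAP*

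**What the plan says.** Protocol section 9.5 reports a June 2020 feasibility count. It puts the rt-PA cohort at about 1561. For the comparison cohort it gives "1037 patients who were admitted to the hospital within 4.5 hours of symptom onset without IVT contraindication and did not receive reperfusion treatment". It fixes the direction of the ratio, "With the treatment ratio 2:1 between the IV rt-PA cohort and the non-reperfusion cohort", and lets the study fall back to 1:1 if 2:1 does not balance the main confounders.

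SAP section 11.1 states that "the 2 cohorts will be 1:1 or 2:1 matched by baseline characteristics using the Propensity Score Matching method", by nearest neighbour with a caliper of 0.2 SD of the logit propensity score. Protocol section 9.7.1 gives the ratio differently: the cohorts "will be 1:1 or 1:2 matched by baseline characteristics using the PSM method". SAP section 10.1 names the R package MatchIt without settings. Neither document says which cohort is matched to which, whether matching is with replacement, in what order it runs, what happens to a control that finds only one partner, or whether matching weights are used.

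The primary comparison "between the 2 PS-matched cohorts will be conducted using a Chi-square test", with a conditional logistic odds ratio alongside. Binary secondary outcomes get the same pair of methods. For the mRS distribution "the Wilcoxon rank sum test and ordinal logistic regression model will be performed". One-year mortality gets a chi-square test, Kaplan-Meier with log-rank, and Cox regression. None of these is described as weighted or stratified. Covariates with an ASD of 0.1 or more after matching go into a multivariable model.

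**The concern.** A pooled comparison of matched cohorts is fair when every set has the same composition. With 1.51 rt-PA patients per control, two partners for every control is impossible, so some controls must be dropped or kept with a single partner. If they are kept, the two-partner sets lie where rt-PA patients are plentiful (high propensity) and the one-partner sets where they are scarce. Counting every matched patient once then over-represents high-propensity patients in the rt-PA cohort only, which brings back part of the difference that matching was meant to remove.

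At stake are the primary chi-square test, the cohort percentages, the mRS rank-sum test, the mortality curves with their log-rank test, and the ordinal and Cox models if they are run unweighted. An unstated software setting would decide whether they are biased.

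**Working it through.** **Inputs.** Protocol 9.5: 1561 rt-PA and 1037 control patients; assumed favourable outcome 28% versus 19.2%; 90% power; two-sided alpha 0.05; 15% loss. SAP 11.1: caliper 0.2 SD. Not in the documents, so assumed: the separation of the cohorts on the propensity index and the strength of the confounder.

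**1. The plan's own sample size.** With r rt-PA patients per control, n0 = [1.96·√(p̄q̄(1+1/r)) + 1.2816·√(p0q0 + p1q1/r)]² / (p1−p0)².
- r = 2: p̄ = (2×0.28 + 0.192)/3 = 0.2507; n0 = (1.96×0.5308 + 1.2816×0.5059)²/0.088² = 368.2, so 369, and 3×369 = 1107 (stated 1106).
- r = 1: p̄ = 0.236; n = (1.96×0.6005 + 1.2816×0.5973)²/0.088² = 487.2, so 488, and 2×488 = 976 (stated 974).
- Loss: 1106/0.85 = 1301.2 and 974/0.85 = 1145.9 (stated 1301 and 1146).

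The figures reproduce to within two patients. Section 9.5 names no test, but this is the formula for the uncorrected chi-square comparison.

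**2. Set counts.**
- Two partners for all controls: 2×1037 = 2074 rt-PA patients, 2074 − 1561 = 513 too few.
- Most complete sets possible: floor(1561/2) = 780, leaving 1037 − 780 = 257 controls (25%) with one partner or none, before the caliper.
- Sets needed for 1301 patients: 1301/3 ≈ 434.

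**3. Why unweighted pooling is biased.** Let set s hold k_s rt-PA patients, and suppose exact matching and no drug effect, so both sides of the set have risk m_s. Over S sets, the pooled rt-PA mean is Σk_s·m_s/Σk_s and the control mean is Σm_s/S. Their difference is Cov(k, m)/k̄. It is zero when k is constant or unrelated to risk. Weighting each rt-PA patient by 1/k_s makes the two means equal.

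**4. Size, by simulation.** Greedy nearest-neighbour matching of controls to up to two rt-PA patients, without replacement, caliper 0.2 SD, one normal confounder, no drug effect. The table assumes a strong confounder (odds ratio 2.7 per SD), random order, and better baseline prognosis in the rt-PA cohort. Differences are in percentage points; ASD is on the confounder.

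| Separation | Second partner taken | 1-partner sets | 2-partner sets | Unweighted difference | 1/k-weighted difference | Unweighted ASD |
|---|---|---|---|---|---|---|
| 0.3 SD | in a second round | 521 | 490 | +3.18 | +0.06 | 0.20 |
| 0.5 SD | in a second round | 512 | 442 | +3.72 | +0.10 | 0.23 |
| 0.8 SD | in a second round | 475 | 373 | +3.89 | +0.15 | 0.24 |
| 0.3 SD | at once | 7 | 744 | +0.17 | +0.11 | 0.01 |
| 0.8 SD | at once | 6 | 613 | +0.24 | +0.19 | 0.02 |

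With the milder odds ratios of 1.5-2 per SD and the same separations, matching in rounds gave about 370-490 complete and 465-530 one-partner sets, a spurious difference of 1.0 to 2.8 points, and chi-square type I error of about 8-35%. Unweighted ASD was 0.18-0.27 and weighted ASD at most 0.06. Taking both partners at once gave 0.4 points or less, and 1:1 matching about none. If the rt-PA cohort has the worse prognosis, the sign reverses (−3.34 at 0.3 SD in the strong-confounder setting).

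**5. Order matters too.** Taking both partners at once in descending propensity order left about 130 one-partner sets. There, 1/k weights worsened balance: an index difference of 0.10-0.12 SD, against 0.03 or less unweighted, at 0.3-0.8 SD. At only 0.1 SD separation with odds ratio 2.7, that setting gave an unweighted difference of −1.6 points.

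**6. Do the plan's checks catch it?**
- The 50% rule does not. In the rounds rows the matched share of rt-PA patients runs from (475 + 2×373)/1561 = 78% to (521 + 2×490)/1561 = 96%.
- The ASD rule depends on an unstated choice. Weighted ASDs look balanced. Unweighted ASDs would usually flag the imbalance, but the model adjustment does not reach the chi-square, rank-sum or Kaplan-Meier results.

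**7. Precision (1/n1 + 1/n0).**
- Ceiling: 2:1 gives 1/1560 + 1/780 = 0.00192; 1:1 gives 2/1037 = 0.00193.
- Weighted up-to-two at 0.3 SD (483 complete, 527 single): effective rt-PA n = 1010²/(527 + 483/2) = 1327, so 1/1327 + 1/1010 = 0.00174, against 0.00199 at 1:1. At 0.5 SD: 0.00186 against 0.00210.

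**8. The two ratio statements.** If 1:2 in protocol 9.7.1 means one rt-PA patient to two controls, at most floor(1037/2) = 518 sets exist. That is 518/1561 = 33% of the rt-PA cohort, below the plan's own 50% rule.

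**The case against.** A reader might infer that 2:1 matching is infeasible here, or that matched sets are bound to be mixed. The documents support neither. Nothing requires all 1037 controls to be kept, up to 780 complete sets exist where about 434 are needed, and dropping unmatched patients is ordinary practice. Mixed sets arise in number only under settings that the SAP does not state.

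Other points on the same side:
- 1:1 is a planned alternative, and feasibility is to be judged once the data are in. An unweighted ASD above 0.1 could itself prompt that fallback. This is fair, but the protocol makes the fallback optional and ties it to match quality, and a weighted ASD table would not prompt it.
- The primary and binary secondary odds ratios in the SAP come from conditional logistic regression, which compares within sets. This stands: those estimates are outside the concern.
- Protocol section 9.7 says that no formal hypothesis testing is planned, which lessens the weight of a type I error argument. It also conflicts with the chi-square tests that both documents plan, and the biased percentages and curves remain either way.
- The SAP's silence on weights does not prove that the ordinal and Cox models will be unweighted or unadjusted. This stands, so they are included only conditionally.
- The part of the SAP between 11.1 and 11.3 is redacted, and the protocol's checklist places sensitivity analyses in a section not shown. Corrective analyses may exist there, so the point is limited to the main analysis as readable.

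**Conclusion.** The point holds in conditional form. The counts cannot give every control two rt-PA partners. If incomplete sets are kept, the analyses in SAP 11.1 that pool matched patients without weights retain confounding. The likely size is about 1-3 percentage points against the 8.8-point target, in favour of whichever cohort has the better baseline prognosis. It rests on assumed separation of 0.3-0.8 SD, a prognostic odds ratio of 1.5-2 per SD and approximate feasibility counts; the documents give neither of the first two. Under the other common way of matching, the bias is negligible within those ranges.

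It would go too far to say that the primary result is biased, because the conditional odds ratio is protected and the matching settings are unknown. It is still more than a missing detail: the plan followed as written permits a misleading primary test and misleading mRS and mortality comparisons, and its ASD and 50% rules do not reliably detect this. Should-fix.

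**What to change.** In SAP 11.1, before matching, choose one of two routes.

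1. **Make 1:1 the primary ratio.** The unweighted tests can then stay, and at the ceiling there is no meaningful loss of precision.
2. **Match each control to up to two rt-PA patients**, without replacement, in random order and in rounds. Give each control weight 1 and each rt-PA patient weight 1/k, where k is the number of rt-PA patients of the set who are in that analysis, so that the expected 15% loss is allowed for. Use these weights, with standard errors clustered by set, for the ASDs, cohort percentages, primary test, Kaplan-Meier, Cox and ordinal analyses. Order and rounds must be stated along with the weights, because weights alone can worsen balance under another order. In the scenarios above, this route has roughly 11-13% lower variance than 1:1.

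Under either route, name the focal cohort and reconcile the ratio in protocol 9.7.1 with the one in the SAP. Keeping only complete 2:1 sets is also valid if the selection rule is stated, but after matching in rounds it would cost precision: 370-485 sets give a variance factor of 0.0041-0.0031.

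The cost is SAP wording and weight and cluster options in the code, with no new data.
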